### 3.1.2.2 Treatment Regimens

Induction treatments will be administered in 28-day cycles, as outlined in [Table 2](#). Inpatient dose escalation is not permitted in this study. The starting dose for idasanutlin will be 100 mg QD. The dose for idasanutlin will be increased by at least 50 mg from the preceding dose level. *During the dose-escalation phase, patients will be enrolled according to the schema in [Figure 6](#). Three patients will initially be enrolled in each cohort, and up to 3 additional patients can be enrolled in a cohort at the Sponsor's discretion. The first patient in each cohort will be observed for safety for 1 week after Cycle 1 Day 1 before additional patients are enrolled in the same cohort. A minimum of 3 patients enrolled in a cohort must complete at least the defined DLT window before enrollment commences in the next cohort.*

*Patients in the first cohort will begin with a starting oral dose of 100 mg of idasanutlin QD on Days 1•5 of each cycle in combination with a flat dose of obinutuzumab 1000 mg intravenous (IV) on Days 1, 8, and 15 of Cycle 1 and Day 1 of Cycles 2•6 (see [Table 2](#) and [Figure 11](#) for details on treatment regimens). This regimen is referred to as Regimen A.*

*Following the identification of the MTD for idasanutlin in combination with obinutuzumab, a bridging cohort of DLBCL patients will be opened to test this MTD in combination with rituximab (375 mg/m^2 on Day 1 of each cycle; see [Figure 6](#), [Figure 12](#), and [Table 2](#)).*

*If safety and tolerability allow, idasanutlin dose escalation may be explored in combination with rituximab in patients with DLBCL until identification of a new MTD (see [Figure 6](#)). A different RP2D in combination with rituximab maybe chosen based on a different MTD.*

*Following the identification of the MTD for idasanutlin in combination with obinutuzumab, a bridging cohort of FL patients will be opened to test this MTD in a different regimen, referred to as Regimen B. Obinutuzumab will be given alone in Cycle 1 and in combination with idasanutlin in Cycles 2•6 (see [Figure 6](#), [Figure 12](#), and [Table 2](#)).*

*If safety and tolerability allow, idasanutlin dose escalation may be explored with this Regimen B in patients with FL until identification of a new MTD (see [Figure 6](#)). The RP2D and regimen for patients with FL will be decided at the end of the dose-escalation phase. Two different RP2Ds and/or regimens may apply for FL and DLBCL, respectively.*

*After the last patient in each cohort has completed the DLT observation period, the Sponsor, in consultation with the investigators, will evaluate the next dose recommended according to the modified continual reassessment method with overdose control (mCRM; see [Section 3.1.2.3](#)) and agree on doses for the subsequent cohort,*

*taking into account relevant demographic, adverse event, laboratory, dose administration, and PK (if available) data. At each dose-escalation step, the dose may be escalated, de-escalated, or an additional cohort at the same dose level may be enrolled.*

*During the dose-escalation phase, study treatment will be administered as outlined in [Table 2](#). Patients with FL who achieve a CR or PR at the EOI will also receive maintenance treatment with obinutuzumab. Maintenance treatment should start 8 weeks ( $\pm 1$  week) after Day 1 of the final cycle of induction and will continue until disease progression or unacceptable toxicity for up to 2 years (see [Table 3](#)).*

*Patients with DLBCL who achieve a CR based on modified Lugano 2014 criteria at the end of induction (defined as within 6–8 weeks after the start of the last cycle of study treatment) are allowed to proceed to hematopoietic stem cell transplantation if deemed appropriate by the investigator. Such patients will be followed for disease progression and survival.*

**Table 2 Induction Treatment for Dose-Escalation Phase**

Dose-Escalation, FL and DLBCL Patients (28-Day Cycles): Regimen A	
Cycle 1	DLT period 
 
• Obinutuzumab 1000 mg IV on Days 1, 8, and 15
 
• Idasanutlin, oral Days 1•5, starting dose 100 mg QD, minimal clinically and pharmacologically feasible dose-escalation steps 50 mg
 

Cycles 2•6	
 
• Obinutuzumab 1000 mg IV on Day 1
 
• Idasanutlin, oral Days 1•5, starting dose 100 mg QD
 

Dose-Escalation Bridging Cohort, DLBCL Patients Only (28-Day Cycles)	
Cycle 1	DLT period 
 
• Rituximab 375 mg/m^2 IV on Day 1
 
• Idasanutlin, oral Days 1•5, starting dose MTD identified in combination with obinutuzumab with Regimen A, minimal clinically and pharmacologically feasible dose-escalation steps 50 mg
 

Cycles 2–6	
 
• Rituximab 375 mg/m^2 IV on Day 1
 
• Idasanutlin, oral Days 1•5, starting dose MTD identified in combination with obinutuzumab
 

Dose-Escalation Bridging Cohort, FL Patients Only (28-Day Cycles): Regimen B	
Cycle 1	
 
• Obinutuzumab 1000 mg IV on Days 1, 8, and 15
 

Cycles 2–6	
 
• Obinutuzumab 1000 mg IV on Day 1
 
• Idasanutlin, oral Days 1•5, starting dose MTD identified in combination with obinutuzumab with Regimen A during dose escalation, minimal clinically and pharmacologically feasible dose-escalation steps 50 mg
 

DLT period will be Cycles 1 and 2.	

*DLBCL =diffuse large B-cell lymphoma; DLT = dose-limiting toxicity; FL =follicular lymphoma; IV=intravenous; MTD =maximum tolerated dose; QD=once a day.*

**Table 3 Maintenance Treatment during the Dose-Escalation Phase for Patients with Follicular Lymphoma**

Post-Induction Treatment	
Patients with FL	Maintenance treatment consisting of the following: 
 
• Obinutuzumab 1000 mg IV every 2 months for 24 months
 

*FL = follicular lymphoma; IV = intravenous.*

### **3.1.2.3 Dose-Toxicity Model with mCRM**

The dose escalation will employ a modified-Continual Reassessment Method with Overdose Control (mCRM) design in order to define MTD and/or the recommended dose. The design is based on the primary safety variable (the occurrence of a DLT). The MTD is defined as the dose that maximizes the probability of a DLT being in the targeted toxicity interval of 25%• 35%, subject to the probability of DLT being in the excessive toxicity interval of 35%• 100% being less than 35%. Patients within a cohort will be enrolled in a sequential manner in cohorts of at least 3 patients each, which, if required, can be expanded with additional patients. Each patient will be observed over 1 cycle (1 cycle lasts 28 days) of treatment for DLT assessment. The first patient in each cohort will be observed for safety for 1 week *after Cycle 1, Day 1* before enrolling additional patients in the cohort. After the last patient in each cohort has completed the 1-cycle DLT observation period, the Sponsor and investigators will evaluate the next dose recommended by the mCRM design and agree on the dose for the subsequent cohort. At each dose-escalation step, the dose can be escalated, de-escalated, or an additional cohort at the same dose-level can be enrolled.

The starting dose for idasanutlin will be 100 mg and the fixed dose for obinutuzumab will be 1000 mg. *The dose for rituximab starting from the bridging cohort for DLBCL patients will be 375 mg/m^2.* The dose-escalation is for the dose of idasanutlin. The maximum allowable increments for idasanutlin between dose levels will be as follows:

- 151% increase if the last idasanutlin dose is below or equal to 300 mg
- 33% of relative increase if the last idasanutlin dose is above 300 mg

The dose of idasanutlin will not be escalated above 800 mg. The selection of the next dose will be subject to clinical judgment and mandated safety constraints that limit the size of dose increments. Clinical judgment will always override mCRM recommendations in the dose-selection process.

The model-based dose escalation at each step will identify the next recommended dose level subject to the following criteria:

- The posterior probability of being within the excessive toxicity interval (above 35% DLT probability) is below 35%, and
- The posterior probability of being within the target toxicity interval (of 25%• 35% DLT probability) is maximized.

Note: To fulfill the above statement, a loss function is being defined as per following:

- 0• 25 under dosing
- 25• 35 targeted toxicity
- 35• 60 excessive toxicity
- 60• 100 unacceptable toxicity

Where the “under dosing” and “excessive toxicity” are identically weighted to weight as much as the “unacceptable toxicity”; as such, the “targeted toxicity” will be maximized (i.e., Loss=[1,0,1,2]).

The dose-escalation will stop under the following circumstances:

- The maximum sample size of 40 patients has been reached, or
- At least a minimum of 9 patients across 3 cohorts has been accrued overall, at least 6 patients have been accrued at the MTD dose, and in addition the probability that the MTD dose lies within the target toxicity interval is above 40%.

The dose-toxicity relationship is described by a two-parameter logistic regression model:

$$\text{logit}[p(d_j^*)] = \log(\alpha) + \beta d_j^*$$

where  $p(d_j^*)$  denotes the probability to experience a DLT at dose  $d_j$  (mg), where  $d_j^* = \log(\frac{d_j}{d^R})$  is the transformed (i.e., standardized) dose using the reference dose,  $d^R = 300$ .

The following bivariate log normal prior distribution will be used for  $\alpha$  and  $\beta$  assuming no prior correlation between model parameters:

[figure not shown]
$$\begin{bmatrix} \log(\alpha) \\ \log(\beta) \end{bmatrix} \sim \mathcal{N} \left[ \begin{pmatrix} -1.237 \\ 0.460 \end{pmatrix}, \begin{pmatrix} 2.661 & 0 \\ 0 & 1.816 \end{pmatrix} \right]$$

A graphical representation based on this prior model is shown in [Figure 7](#) and has been constructed to match the skeleton of probability shown in [Table 4](#). This skeleton is based on a model built on an existing study (Study NP27872) and represents the most up-to-date relationship between dose and toxicities.

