### **Determination of Sample Size**

Dose finding will be conducted during the dose-escalation phase of this study. The estimated sample size follows from the dose-escalation rules for a mCRM algorithm, as outlined in the protocol. It is anticipated that enrollment of up to eight cohorts of 3-6 patients each, for a total of 9-40 patients, will be required to establish the RP2D during the dose-escalation phase (See protocol for modeling details). The estimated probability to require more than 30 patients in the investigated scenarios in the protocol is generally less than 5%.

Approximately 80 patients (40 patients with FL and 40 patients with DLBCL) will be enrolled during the expansion phase.

The primary efficacy analysis for the expansion phase will be estimation of the true proportion of patients expected to obtain a PET-defined CR at EOI. A sample size of 40 patients is deemed sufficient to provide adequate precision for the point estimate and for the lower end of the 90% CI to rule out a clinically uninteresting probability of response of <40% in FL (GAUDI study/BO21000) and (Gadolin/GO01297), and 40% in DLBCL assuming an observed PET-defined CR rate of 55%. The protocol provides 90% Clopper-Pearson exact CIs for the probability of achieving an EOI PET-defined CR for a range of observed proportions based on a sample of 40 patients.

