### **6.1 DETERMINATION OF SAMPLE SIZE**

Dose finding will be conducted during the dose-escalation phase of this study. The estimated sample size follows from the dose-escalation rules for a mCRM algorithm, as outlined in Section 3.1. It is anticipated that enrollment of up to eight cohorts of 3•6 patients each, for a total of 9•40 patients, will be required to establish the RP2D during the dose-escalation phase (See [Appendix 11](#) for modeling details). The estimated probability to require more than 30 patients in the investigated scenarios in [Appendix 11](#) is generally less than 5%.

Approximately 80 patients (40 patients with FL and 40 patients with DLBCL) will be enrolled during the expansion phase.

The primary efficacy analysis for the expansion phase will be estimation of the true proportion of patients expected to obtain a PET-defined CR at EOI. A sample size of 40 patients is deemed sufficient to provide adequate precision for the point estimate and for the lower end of the 90% CI to rule out a clinically uninteresting probability of response of <40% in FL (GAUDI study/BO21000 and Gadolin/GO01297), and 40% in DLBCL assuming an observed PET-defined CR rate of 55%. [Table 22](#) provides 90% Clopper-Pearson exact CIs for the probability of achieving an EOI PET-defined CR for a range of observed proportions based on a sample of 40 patients.

**Table 22 Potential 90% CI for the True Probability of Achieving a PET-CT• Defined Complete Response at End of Induction for n=40**

Observed Proportion of Patients Achieving a PET-CT• Defined CR at EOI	Two-Sided 90% Clopper-Pearson CI a for True Population PET-CT• Defined CR
0.32	(0.20, 0.46)
0.50	(0.36, 0.64)
0.55	(0.40, 0.68)
0.60	(0.46, 0.73)
0.65	(0.51, 0.77)
0.70	(0.56, 0.82)
0.72	(0.58, 0.83)
0.75	(0.61, 0.86)
0.80	(0.66, 0.89)
0.85	(0.72, 0.93)

CR=complete response; CT=computed tomography; EOI=end of induction; PET=positron emission tomography.

a Note that the lower limit of a two-sided 90% CI is equivalent to a one-sided 95% CI limit.

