**Table 1                      Details of Scenario 5**

Dose	50	100	150	200	250	300	350	400	450	500	550	600	650	700	750	800
Prior Guess of Risk (%)	3	8	15	22	30	40	45	50	55	60	65	70	75	80	90	100

In Table 2 it is seen that the design under Scenario 1 selected a dose with true risk of toxicity within 25%•35%, approximately 48% of the time (so above the specified 40%). In addition, this selection is done with help of 38% of patients over 500 simulated studies. It is also noticeable that the percentage of patients in excessive toxicity range (or unacceptable toxicity) remains below the specified 35% (i.e., 24%). Scenario 2 and Scenario 4 represent cases where the true toxicity is a lot higher than expected. This explains the relatively high proportion of patients being in the excessive or unacceptable dose range; however, it is seen in Table 3 that the maximum doses tested are 300 mg and 400 mg, respectively, which is acceptable from a clinical perspective. Scenarios 3 and 6 have true toxicities lower than expected (30% and 80% lower, respectively), as it could be seen in the relative low proportion of patients being in the excessive or unacceptable toxicity. In addition, the dose recommended for Scenario 6 is the

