## Appendix 11 Simulations among the Statistical Design of mCRM (cont.)

maximum dose tested (i.e., 800 mg), which is unexpected from a clinical perspective. This dose is recommended with the help of a maximum of 45 patients as seen in [Table 3](#).

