**Table 2 Probability of Dose-Limiting Toxicities under Various Scenarios**

Scenario/True Toxicity	%	Probability of DLT Obtained over Simulations of 500 Studies		
		Under-Dosing (0, 0.25)	Targeted Toxicity (0.25, 0.35)	Excessive Toxicity (0.35, 1)
1/Prior guess	Experimentation	37%	38%	24%
	Recommendation	16%	48%	35%
2/30% higher than prior guess	Experimentation	32%	17%	50%
	Recommendation	12%	24%	63%
3/30% lower than prior guess	Experimentation	65%	31%	2.9%
	Recommendation	46%	49%	3.8%
4/80% higher than prior guess	Experimentation	26%	14%	59%
	Recommendation	9.8%	23%	67%
5/toxicity increase on the tail of prior guess	Experimentation	39%	39%	21%
	Recommendation	18%	52%	29%
6/80% lower than prior guess	Experimentation	100%	0%	0%
	Recommendation	100%	0%	0%
7/correlation of 0.5 in the covariance matrix	Experimentation	51%	30%	18%
	Recommendation	29%	45%	25%

In [Table 3](#) it is seen that the design under Scenario 1 (selected design) recommends a dose with a sample size within 9• 24 patients over the 500 simulated studies. In addition, it is noticeable that under a toxicity corresponding to 30% lower than expected toxicity, the sample size remains below 40 patients and below 45 patients for a toxicity 80%.

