**Table 3 Operating Characteristics of the Design under Various Scenarios**

Scenario/True Toxicity	True MTD (Simulated)	Maximum Dose Tested *	Selected Dose*	Recommendation of Selected Dose * (%)	Sample Size* [min, n, max]
1/Prior guess	250 mg	400 mg	250 mg	48%	[9, 13, 24]
2/30% higher than prior guess	200 mg	400 mg	250 mg	49%	[9, 13, 24]
3/30% lower than prior guess	350 mg	750 mg	300 mg	44%	[9, 14, 39]
4/80% higher than prior guess	150 mg	350 mg	200 mg	33%	[9, 15, 27]
5/toxicity increase on the tail of prior guess	250 mg	650 mg	250 mg	52%	[9, 13, 30]
6/80% lower than prior guess	>800 mg	800 mg	800 mg	33%	[12, 30, 45]
7/correlation of 0.5 in the covariance matrix	250 mg	500 mg	250 mg	45%	[9, 15, 33]

\* Over 500 simulated studies.

[figure not shown]

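### The 40% stopping clause in Section 3.1.2.3 cannot be met before about 24 patients with the printed prior, so Appendix 11 and the below-5% statement in Section 6.1 do not describe the written rule

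*Combined protocol and SAP*

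**What the plan says.** Section 3.1.2.3 gives two ways to stop escalation. The first is "The maximum sample size of 40 patients has been reached". The second needs three things together: at least 9 patients across 3 cohorts, at least 6 at the MTD, and "the probability that the MTD dose lies within the target toxicity interval is above 40" percent. The target interval is a DLT probability of 25% to 35%.

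The synopsis states: "The estimated probability to require more than 30 patients in the investigated scenarios in the protocol is generally less than 5" percent. Section 6.1 repeats this and refers to Appendix 11.

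Appendix 11 Table 3, "Operating Characteristics of the Design under Various Scenarios", lists sample size as [min, n, max] over 500 simulated studies: [9, 13, 24] in Scenarios 1 and 2, [9, 14, 39], [9, 15, 27] and [9, 13, 30] in Scenarios 3 to 5, [12, 30, 45] in Scenario 6 and [9, 15, 33] in Scenario 7.

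The Appendix 11 text on Table 2 says that Scenario 1 selects an in-target dose "approximately 48% of the time (so above the specified 40" percent). Of Scenario 6 it says: "This dose is recommended with the help of a maximum of 45 patients".

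**The concern.** A posterior probability above 40% for an interval only 10 percentage points wide is a demanding precision criterion, and 9 to 13 patients carry little information about a DLT rate near 30%. If the clause cannot be met at the sizes in Table 3, then the stated escalation size, the below-5% statement and the dose-selection and overdose frequencies in Table 2 belong to some other rule. The safety operating characteristics of the design as written would then be undocumented.

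There is also a question of patient numbers. Section 3.1.2 plans about 9 to 40 patients for the whole escalation phase. Section 3.1.2.2 adds a DLBCL bridging part and an FL Regimen B bridging part, with 3 patients initially in each cohort, and Section 3.1.2.3 gives them a similar mCRM. A Regimen A part much larger than Table 3 suggests could leave too few patients for these, if the 40 covers the phase.

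**Working it through.** **Inputs (Section 3.1.2.3, Table 4, Appendix 11).** Model: logit p(d) = log α + β·log(d/300). Prior: log α and log β independent normal, means −1.237 and 0.460, matrix entries 2.661 and 1.816. Appendix 11 calls this matrix a covariance, so the entries are read as variances. Doses are 50 to 800 mg in 50 mg steps, starting at 100 mg. Increments are at most 151% up to 300 mg and 33% above. Overdose limit: P(p > 0.35) below 0.35. True toxicity curves are those of Appendix 11.

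**Quantity in the clause.** With n patients and y DLTs at each dose, the posterior is proportional to prior × Π p(d)^y · (1 − p(d))^(n − y). The clause needs T = P(0.25 < p(MTD) < 0.35 | data) > 0.40.

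**Step 1: ceiling on T.** All patients at one dose, maximised over dose and outcome:

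| Reading of the printed matrix | N=9 | N=18 | N=21 | N=24 |
|---|---|---|---|---|
| Variances | 0.28 | 0.373 | 0.396 | 0.419 |
| Standard deviations | 0.27 | 0.364 | 0.388 | 0.416 |
| Precisions | 0.39 | 0.449 | 0.471 | 0.492 |

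Under the variance reading the maxima occur at 300 mg, with 3 DLTs in 9, 6 in 18, 7 in 21 and 7 in 24. Following paths the design can actually take gives nothing higher: at most 0.37 at N=18 with mixed cohorts of 3 to 6, and with cohorts of 3, 0.390 at N=21 and 0.414 at N=24. A non-exhaustive search with free dose allocation reached 0.37 at N=18 and 0.395 at N=21.

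**Step 2: the reported minimum of 9.** With 3 patients at 100 mg and 6 at the evaluated dose, over all doses and outcomes, the largest T is 0.273 (variances), 0.260 (standard deviations), 0.38 (precisions) and 0.270 (variances, with prior means refitted to Table 4). None reaches 0.40.

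**Step 3: a check without the model.** If the posterior is roughly normal and centred at 30%, more than 40% of its mass lies within ±5 points only if 5/SD > 0.524, so SD < 9.5 points. A binomial proportion at 30% has that SD when 0.30 × 0.70 / n = 0.0954², that is n ≈ 0.21 / 0.0091 ≈ 23 patients at that dose.

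**Step 4: simulation of the full rule.** Variance reading, cohorts of 3, cap 40. Ranges cover both selection rules in the protocol (maximum target probability, or the loss function) and different numerical grids and runs.

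| | Table 3 / Section 6.1 | Written rule | 40% clause removed |
|---|---|---|---|
| Scenario 1, smallest N | 9 | 24 to 27 | 9 |
| Scenario 1, mean N | 13 (labelled only n) | 33 to 35 | 14 to 16 |
| Scenario 1, N > 30 | generally below 5% | 56% to 73% | below 1% |
| Scenarios 2 to 5, mean N | 13 to 15 | 33 to 38 | 14 to 17 |
| Scenarios 2 to 5, N > 30 | generally below 5% | 57% to 91% | at most 3% |

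Under the written rule, Scenario 1 trials stop by 24 patients in only 2% to 4% of cases, whereas Table 3 gives 24 as the maximum. In 24% to 35% the clause is never met and the trial runs to 40. Without the clause the sizes are close to Table 3 in Scenarios 1 to 5. Scenario 6 is not reproduced: without the clause the mean is 24 (maximum target probability) or 15 (loss function), against 30.

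**Step 5: what Appendix 11 shows by itself.** It compares 48%, the share of simulated trials that select an in-target dose, with a specified 40%. In Section 3.1.2.3 the 40% is a probability within one trial. It also reports up to 45 patients against a cap of 40.

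**Step 6: room for bridging.** Under the written rule, Regimen A uses more than 34 patients in 49% to 56% of Scenario 1 trials. If the 40 covers the phase, fewer than 40 − 34 = 6 remain, and one initial cohort of 3 in each bridging part needs 6.

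**The case against.** The strongest reply is that the printed prior may not be the one simulated. Its median DLT risk is 14% at 250 mg and 22% at 300 mg, against 30% and 38% in Table 4, which it is said to match. No version tried reproduces every dose path in the text around Table 5. This stands: the prior itself needs reconciling, and the simulated sizes are conditional on it. It does not restore Table 3. Refitting the means to Table 4 with the printed variances gives larger trials in Scenario 1 (mean 36 to 37, more than 30 patients in 76% to 84%).

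The precision reading is more favourable. The clause can then be met from 12 patients, the mean is about 20, and only 2% to 3% of Scenario 1 trials exceed 30, which agrees with Section 6.1. But a minimum of 9 stays impossible and only about 1% of trials stop by 13, so [9, 13, 24] is still not obtained. That reading also conflicts with the word covariance. And it recommends 250 mg after 1 or 2 DLTs in 3 patients at 100 mg, where Section 3.1.2.3 gives 100 mg and 50 mg.

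Three further points stand. The percentages move with the numerical grid, so they give direction and rough size only. The simulation code is not in the documents, so why Table 3 differs is inference. And every recomputed size lies within the planned 9 to 40, so the cap is not breached; the bridging shortfall arises only if that cap covers the whole phase.

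**Conclusion.** The concern holds. With the printed model and prior read as variances, the 40% clause cannot be met at 9 to 18 patients, falls just short at 21 and is first realistically met at about 24. In Scenario 1 the written rule needs about 34 patients on average, not 13, and exceeds 30 in more than half of trials. A minimum of 9 is unattainable under every reading of the prior that was tested, and the different use of the 40% and the 45 patients are visible in Appendix 11 without any simulation. The written stopping rule and its stated performance cannot both be right, so this must be corrected. The exact sizes rest on the printed prior, cohorts of 3 and a cap of 40. The Table 2 frequencies were not recomputed; the point is that they cannot be attributed to the written rule.

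**What to change.** Reconcile Section 3.1.2.3 with Section 6.1, the synopsis and Appendix 11 in one of two ways:

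- Re-run Appendix 11 with exactly the stopping rule, prior and 40-patient cap that will be used. Restate Tables 2 and 3, the expected size and range, and the probability of more than 30 patients from that run.
- If the simulated rule was the intended one, state that rule in Section 3.1.2.3.

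In either case, correct the description of the 40% in Appendix 11. Confirm that the printed prior is the one simulated, checking it against Table 4, the worked dose paths and Table 5. Say whether the 40-patient cap also covers the bridging cohorts. The figures given here are diagnostic and should not be copied into the protocol.

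The cost is a simulation re-run and protocol wording. Keeping the written rule makes the stated sizes less favourable; adopting the simulated one gives up the precision criterion for the MTD. The cap need not change.
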